### **11.4.1 Primary Efficacy Analysis**

The primary efficacy analysis is the analysis of the PDC for three CHF medications (ACEi/ARB, BB and MRA). The pharmacy claims data are provided by data processing centres and health insurance funds. If health insurance data are not available for all patients, an analysis will be performed comparing the data from health insurance funds and data processing centres. The analysis will be adjusted for data from health insurance funds (yes/no).

The PDC will be analysed by a two-sided stratified Wilcoxon signed-rank test (van Elteren test) on a two-sided level of significance of 5%.

The following hypothesis will be tested:

$H_0: m_i = m_c$  vs.  $H_1: m_i \neq m_c$ ,

Where  $m_i$  denotes the median value of the intervention group and  $m_c$  denotes the median value of the control group.

Although statistical guidelines ("Points to consider on adjustment for baseline covariates") suggest adjusting the analysis for all stratification variables of the randomization process, this is omitted. It is desired to get a robust result, if one treatment regimen is favourable to the other across all stratification factors. Nevertheless, supportive analyses adjusting for the stratification factors will be conducted as sensitivity analyses.

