2.3 Per-protocol population

The per-protocol (PP) population consists of all subjects of the ITT population who completed the study without major protocol violations – that are violation of inclusion criteria, meeting any exclusion criteria, post-baseline data not available, consolidated medication plan not available (intervention group patients only) and terminated the study prematurely (except death).

The following protocol violations are defined as major and will lead to exclusion from the PP population:

- Terminated the study prematurely (except death) within the first twelve months

This will result in the following sizes of the analysis populations:

Table 3 Major protocol violation and per-protocol population

Population	Intervention group	Control group	Total
Randomized	130	128	258
ITT	110	127	237
- patients excluded: termination within the first twelve months	8	2	10
withdrawal of informed consent	6	1	7
discontinued	2	1	3
PP	102	125	227

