5.5 Pharmacy claims data from data processing centres and health insurance funds

All known German data processing centres (Apothekenrechenzentren) will be asked to send pharmacy claims data of prescribed medicinal products dispensed at community pharmacies for PHARM-CHF patients to the cost of any statutory health insurance (SHI) funds for the whole study duration and additionally for the measurement of baseline adherence for the 183 days before randomization. In addition, health insurance funds (SHI and private) will be asked to provide data about reimbursed medicinal products dispensed at community pharmacies for the same period. The prescribed medicinal product together with dispensing date and the source of information will be documented.

For patients with withdrawal of informed consent no pharmacy claims data will be available. Therefore, the PDC for these patients cannot be calculated.

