7.8 Primary efficacy analysis

The primary efficacy analysis is the analysis of the PDC between baseline (day of randomization) and 365 days. The pharmacy claims data will be provided by data processing centres and health insurance funds. However, health insurance data were not available for all patients included in the study. Differences between patients with data from data processing centres and data from health insurance funds cannot be excluded. Therefore, an analysis will be performed comparing the data from health insurance funds and data processing centres. The analysis will be conducted twice. On the one hand, the analysis will be adjusted for data from health insurance funds (yes/no). And on the other hand, the analysis will be adjusted for data from health insurance funds (yes/no) and for baseline adherence (yes/no).

Analysis adjusted for data from health insurance funds only

The PDC (adjusted for data from health insurance funds only) will be analysed by a two-sided stratified Wilcoxon signed-rank test (van Elteren test) on a two-sided level of significance of 5%. The level of significance will not be divided among further hypotheses.

The following hypothesis will be tested:

$H_0: m_i = m_c$ vs. $H_1: m_i \neq m_c$,

Where m_i denotes the median value of the intervention group and m_c denotes the median value of the control group.

The following SAS code can be used:

```
proc freq data=xxx;  
    table updated*treatment group*PDC / cmh scores=modridit noprint;  
run;
```

Analysis adjusted for data from health insurance funds and baseline adherence

The PDC (adjusted for data from health insurance funds and baseline adherence) will be analysed by an analysis of covariance (ANCOVA). Treatment group will serve as a fixed effect and baseline adherence will serve as a random effect. Treatment groups will be compared on a two-sided level of significance of 5%. The level of significance will not be divided among further hypotheses.

The following hypothesis will be tested:

H0: $\mu_i = \mu_C$ vs. H1: $\mu_i \neq \mu_C$,

Where μ_i denotes the mean value of the intervention group and μ_C denotes the mean value of the control group.

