The primary analysis population for both adjustment types is the ITT population. However, the primary analysis (both adjustments) will be repeated for the PP population for sensitivity. As a further sensitivity analysis an analysis of (co)variance (AN(C)OVA) for the PDC will be done with PDC as dependent variable, and the further fixed effects treatment (intervention vs. control), data from health insurance funds (yes/no), sex (male vs. female), age (≤ 75 vs. > 75 years), NYHA functional class (I and II vs. III and IV), PHQ-9 score (score < 10 vs. ≥ 10) and diabetes mellitus (yes vs. no). The study region will be omitted since this may lead to an over determination of the analysis model.

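### The baseline-adjusted ANCOVA in SAP 7.8 does not fix its model terms: insurance data has no stated role, baseline adherence is called random, and its form (continuous, 80% or 88%) is left open

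*SAP*

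**What the plan says.** The introduction to SAP 7.8 says the PDC analysis is run twice. The second run is "adjusted for data from health insurance funds (yes/no) and for baseline adherence (yes/no"). The sub-heading names both adjusters again, and so does the method sentence: "The PDC (adjusted for data from health insurance funds and baseline adherence) will be analysed by an analysis of covariance (ANCOVA"). The roles are then assigned in a single sentence: "Treatment group will serve as a fixed effect and baseline adherence will serve as a random effect". No SAS code follows, whereas the van Elteren test has some.

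On status, SAP 7.8 takes the ITT population as primary for both adjustment types and adds that "the primary analysis (both adjustments) will be repeated for the PP population for sensitivity". Each of the two is tested at an undivided two-sided 5%. Protocol 11.4.1 names only one test for this variable: "The PDC will be analysed by a two-sided stratified Wilcoxon signed-rank test (van Elteren test"). The ANCOVA is therefore specified in the SAP alone.

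Three other places bear on the wording:

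- The sensitivity AN(C)OVA in SAP 7.8 lists "the further fixed effects treatment (intervention vs. control), data from health insurance funds (yes/no") among its terms, but does not include baseline adherence.
- The quality-of-life ANCOVA in SAP 7.10.1.2 takes treatment as fixed effect and the baseline score as covariate.
- SAP 5.3 and 5.6 measure baseline adherence as a PDC over the 183 days before randomization, and categorise all PDC values, baseline included, at both 80% and 88%. SAP 5.8.1 applies the label adherent to a PDC of at least 80% and keeps 88% for sensitivity, in both cases for follow-up PDC.

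**The concern.** Two analysts working from SAP 7.8 could fit different models and each claim to have followed it.

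- **Insurance data.** It is announced as an adjuster but has no place in the term list.
- **Random effect.** This is not how a baseline covariate enters an ANCOVA, and it differs from the SAP's own quality-of-life model.
- **Baseline adherence (yes/no).** Section 7.8 points to neither of the two cut-offs that the SAP plans for baseline PDC. Nor does it explain why the continuous value, also planned, is set aside.

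What is at stake is a reproducible specification of an analysis that the SAP labels primary, and the only one of the two that uses baseline adherence. SAP 7.10.1.1 repeats the primary analyses by drug class, so the gap carries over. There is also a cost in precision, because a split at a cut-off discards part of what baseline PDC can explain.

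**Working it through.** **Planning figure.** SAP 1.2 gives difference 0.10, SD 0.22, two-sided t-test, alpha 5%, power 85%. The noncentral t gives 85.05% at 88 per group, so N = 176 reproduces. Planning is not in question.

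**Patients available.** SAP 2.2 gives an ITT population of 110 vs 127. For patients who withdrew consent, SAP 5.5 says: "Therefore, the PDC for these patients cannot be calculated". In Table 3 (SAP 2.3), under "patients excluded: termination within the first twelve months", 6 and 1 are consent withdrawals. So at most 110 − 6 = 104 and 127 − 1 = 126 patients have a PDC, 230 in all.

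**Assumptions.** Baseline PDC is taken as normal with mean 0.70 and SD 0.22 (the values in SAP 1.2). The correlation r between baseline and follow-up PDC is not in the documents; I use 0.3, 0.5 and 0.7.

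**Formulas.** Relative to no adjustment, the variance of the treatment effect is

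- continuous baseline: 1 − r²
- baseline split at a cut-off: 1 − (r·k)², where k = φ(z)/√(p(1 − p)), z = (cut-off − 0.70)/0.22 and p = P(baseline ≥ cut-off).

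At 80%: z = 0.4545, p = 0.3247, k = 0.7683. At 88%: z = 0.8182, p = 0.2066, k = 0.7050.

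The unadjusted SE is 0.22 × √(1/104 + 1/126) = 0.0291, which gives 92.7% power (df = 228). ANCOVA power uses the noncentral t with df = 230 − 4 = 226.

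| r | 1 − r² | 1 − (rk)² at 80% | Variance ratio | SE continuous | SE split at 80% | Power continuous | Power split at 80% |
|---|---|---|---|---|---|---|---|
| 0.3 | 0.910 | 0.947 | 1.04 | 0.0278 | 0.0284 | 94.8% | 94.0% |
| 0.5 | 0.750 | 0.852 | 1.14 | 0.0252 | 0.0269 | 97.6% | 95.9% |
| 0.7 | 0.510 | 0.711 | 1.39 | 0.0208 | 0.0246 | 99.8% | 98.2% |

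Put as patients, 230 analysed with the 80% split give the precision of 230/1.0405 = 221, 230/1.1366 = 202 or 230/1.3936 = 165 analysed with continuous PDC. The half-width of the 95% CI goes from 0.055, 0.050 and 0.041 to 0.056, 0.053 and 0.048.

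**Which cut-off.** At 88% the variance ratios are 1.05, 1.17 and 1.48. Against the 80% split, the SE rises by 0.4, 1.4 and 3.2%.

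**Shape of the PDC.** PDC is bounded, so the formula was checked by simulation with beta-shaped values of the same mean and SD (104 vs 126, 1,000 trials per setting). At 80% the ratios were 1.04, 1.13 and 1.37, close to the normal case.

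**Movement of the estimate.** In 150 simulated trials at r = 0.5, with an assumed even split on insurance data, the treatment difference under an 80% or 88% split departed from the continuous-covariate result with an SD of about 0.01 PDC and a maximum of about 0.03. The planned effect is 0.10.

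**Random or fixed.** With the same baseline term entered as random instead of fixed, the simulated variance ratio was 0.9995 to 1.0000.

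**Insurance data.** The effect of leaving it out cannot be computed: the documents give neither the share of patients with such data nor its relation to PDC.

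**The case against.** The strongest reply is that most of this is already settled by the text.

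- **Insurance data.** The introduction, sub-heading and method sentence all name it. The role sentence can be read as covering treatment and the newly added baseline term only. That stands: this is a drafting gap. A reader might infer that the adjustment was dropped, but three statements of intent say otherwise.
- **Random effect.** The label changes nothing material. That stands too.
- **Cut-off.** A reader might infer that the SAP has no cut-off for baseline PDC. It has two, in SAP 5.3 and 5.6, and the adherent label makes 80% the likely choice. What remains is that 7.8 does not say which planned form it uses. Reading yes/no as baseline data available or not is also possible, because that is what the words mean for insurance data in the same sentence. It is strained, since SAP 5.6 defines baseline adherence as a PDC.
- **Weight.** A split covariate is a legitimate choice. It still beats the unadjusted analysis (94.0 to 98.2% against 92.7% power), and the protocol's own test does not depend on it. That stands. The power cost would look larger at the planned 88 per arm, but the SAP already reports an ITT population of 110 vs 127, so that is not the relevant size.

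The reply does not remove the core: an analysis that the SAP counts as primary lacks a complete term list and a defined baseline term, and a more precise form is available from data already planned.

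**Conclusion.** The point holds as a specification gap with a modest cost in precision, and it should be fixed. Section 7.8 gives insurance data no role in its only term sentence, mislabels the baseline term and does not name that term's form.

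The yes/no form at 80% inflates the variance of the treatment effect by a factor of 1.04 to 1.39 and costs 0.8 to 1.7 percentage points of power at 104 vs 126. These figures rest on the assumed correlations, an approximately normal baseline PDC, and no missing PDC beyond the consent withdrawals in Table 3.

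A reader might go on to infer that the primary result would be biased or underpowered. The documents do not support that: no bias is shown, power stays at about 94% or more under either form, and the van Elteren test and N = 176 are untouched.

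**What to change.** Make two edits in SAP 7.8.

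1. Replace the term sentence with: *ANCOVA of the 365-day summary PDC with treatment and insurance data (yes/no) as fixed effects and the continuous 183-day baseline summary PDC as a covariate; report the adjusted mean difference with 95% CI; count by arm the patients left out for lack of a baseline PDC.*
2. Delete (yes/no) after baseline adherence in the introduction.

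If the team prefers a yes/no covariate, the minimum is to name the cut-off in 7.8 and list that factor and insurance data as fixed effects.

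The change needs no protocol amendment, new data or further patients. One small downside is that, with no substitution of missing values (SAP 6.1), patients without a baseline PDC drop out of this model. A yes/no split at a PDC cut-off would lose the same patients; only under the availability reading would the yes/no model keep them, and their number is not in the documents.

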1.2 Sample size considerations

Assuming a baseline PDC for cardiovascular medication of 0.7 and a standard deviation of the PDC of 0.22 a sample size of N=176 (88/group) patients is needed to detect a 10% difference between the intervention group and the usual care group with a power of 85% and an alpha of 5%. Assuming a dropout and lost to follow-up of 30% N=248 patients have to be enrolled in the study. The planning is based on a two-sided t-test and performed by means of SAS Version 9.4.

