1.4 Randomization

Eligible patients are assigned in a 1:1 ratio to the intervention or control group. Minimization with 20% residual randomness is used to ensure balance of the following characteristics: Gender (male/female), age (≤ 75 , > 75), NYHA functional class (I and II, III and IV), PHQ-9 (score < 10 , ≥ 10), diabetes mellitus (yes/no), study region (according to regional Associations of Statutory Health Insurance Physicians (KV-Region)).

A web-based randomization tool developed by IZKS Mainz is used within this study allowing investigators to randomize patients via a secure web interface.

Subjects withdrawn from the study retain their identification codes (i.e. patient number). New subjects must always be allotted a new identification code.

2 Analysis populations

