5.6 Primary efficacy variable

The primary efficacy variable is medication adherence, pre-specified as a significant difference of the proportion of days covered (PDC) between the intervention and control group using pharmacy claims data for three CHF medications [angiotensin-converting enzyme inhibitors or angiotensin receptor blockers (ACEi/ARB), β -blockers (BB), and mineralocorticoid receptor antagonists (MRA)] prescribed at baseline.

Medication adherence will be calculated based on the PDC during the 365-days following randomization. The dose information documented at screening / visit 1 or in case of switches at visit 3 will be used. Medication switches, stockpiling, inpatient days (hospital stays), medication fills prior to randomisation, and death will be considered. To measure baseline adherence, the PDC for the period 183-days before randomization to randomization for each drug class (ACEi/ARB, BB, MRA) will be analysed.

In case of inpatient days, the proportion will be adjusted by excluding days from both the numerator and denominator assuming that patients did not deplete their medication on their medication supply on those excluded days. If a patient switches medications within a class (including ACEi/ARB), the patient's medication supply will be replaced with the new medication supply. If a patient dies, all days following the death will be censored.

Existing medication at randomization (=day 1) and medication dispensed during 14 days after randomization (=day 1) will be considered if at least one additional dispensing occurred during the 365-days follow-up. Existing medication at randomization will be captured, but only the days during the 365-days follow-up will contribute to the final proportion.

Adherence for all three CHF medication classes, if prescribed, will be calculated and can range from 0 to 1.0 (perfect adherence) and will then averaged across all non-missing classes of medications to derive the summary PDC.

PDC:

- PDC at Baseline (183 days), 365 days, 730 days and Individual Follow-up time
- PDC ACEI/ARB at Baseline (183 days), 365 days, 730 days and Individual Follow-up time
- PDC BB at Baseline (183 days), 365 days, 730 days and Individual Follow-up time
- PDC MRA at Baseline (183 days), 365 days, 730 days and Individual Follow-up time
- PDC statins at Baseline (183 days), 365 days, 730 days and Individual Follow-up time
- *Derived: all PDC-values will be categorized as: < 80% and ≥ 80% and < 88% and ≥ 88%*

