7.11 Subgroup analyses

Exploratory subgroup analyses will be performed for the primary efficacy and primary safety variables. Additionally, subgroup analyses for the PDC of each drug class, the mean PDC $\geq 80\%$, all-cause mortality or unplanned cardiovascular hospitalizations as recurrent event, unplanned cardiovascular hospitalizations as recurrent event, and all-cause mortality will be performed.

Each subgroup and the corresponding interaction with treatment group will be included into the analysis model (the PDC of each drug class will be analysed by an ANOVA,

for the mean PDC $\geq 80\%$ a logistic regression model will be used). The following subgroups are planned:

- Minimization-criteria:
 - o Sex (male/female),
 - o Age (≤ 75 , > 75 years),
 - o NYHA functional class (I and II, III and IV),
 - o PHQ-9 (depression score < 10 , ≥ 10),
 - o Diabetes mellitus (yes/no),
- Time between last heart failure hospitalization and randomization (< 3 months vs. ≥ 3 months) Number of different drug substances (median at randomisation), as an indicator of the level of illness burden
- Number of different co-morbidities (median at randomisation), as a further indicator of the level of illness burden
- Heart failure medication at baseline (BB versus BB plus ACEi/ARB, BB plus ACEi/ARB versus BB plus ACEi/ARB/MRA) (subpopulations)
- Heart rate at baseline (≤ 75 vs. > 75 min^{-1})
- QoL score (MLHFQ Median)
- HFrEF vs. HFmrEF/HFpEF (LVEF $< 40\%$ vs. $\geq 40\%$)

The subgroup analyses will be displayed by the interaction term as well as descriptive statistics by subgroup.

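### The PDC sensitivity model with the minimisation factors and the PDC subgroup ANOVAs do not name baseline PDC (the subgroup models also omit insurer data), which costs precision in supportive and exploratory analyses only

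*SAP*

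**What the plan says.** Baseline adherence is derived from claims data. SAP 5.6 states: "To measure baseline adherence, the PDC for the period 183-days before randomization", for each of the three drug classes, and its list of PDC variables also contains a baseline summary value.

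SAP 7.8 plans the primary van Elteren test, stratified by availability of insurer data. It adds an ANCOVA adjusted for insurer data and baseline adherence. SAP 7.10.1.1 repeats the primary analyses for each class.

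Two further sets of PDC models follow:

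- **Sensitivity model, SAP 7.8.** Here "an analysis of (co)variance (AN(C)OVA) for the PDC will be done with PDC as dependent variable, and the further fixed effects treatment". The other listed terms are insurer data, sex, age group, NYHA group, PHQ-9 group and diabetes. Baseline PDC is not listed. The only omission explained is study region.
- **Subgroup models, SAP 7.11 and Protocol 11.4.5.** Subgroup and its interaction with treatment enter the model, and "the PDC of each drug class will be analysed by an ANOVA". Neither baseline PDC nor insurer data is named. SAP 7.11 also announces subgroup analyses of the primary efficacy variable, but names no model for summary PDC.

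**The concern.** The pre-randomisation value of an outcome is usually among its better predictors. Here it is derived for the summary and for each class, and SAP 7.8 itself uses baseline adherence as an adjuster. As listed, no planned model holds the minimisation factors and baseline PDC together, and no subgroup model uses baseline PDC at all.

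The subgroup models also drop insurer data without comment, although SAP 7.8 adjusts for it because differences between the data sources cannot be ruled out.

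At stake is the width of the intervals in one robustness model and the power of interaction tests that are weak to begin with.

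**Working it through.** **Inputs**

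- SD 0.22, difference 0.10 and 88 per group, SAP 1.2: "a standard deviation of the PDC of 0.22 a sample size of N=176 (88/group) patients is needed to detect a 10% difference".
- Power and level, SAP 1.2: "with a power of 85% and an alpha of 5" per cent. Test: "The planning is based on a two-sided t-test and performed by means of SAS Version 9.4".
- Patients: ITT 110 v 127 (SAP Table 2). SAP Table 3 shows 6 and 1 withdrawals of consent within twelve months, and SAP 5.5 says PDC cannot be calculated after withdrawal. So 110 − 6 = 104 and 127 − 1 = 126. This is an upper bound, since a later withdrawal or missing claims data would reduce it further.
- Correlation r between baseline and 365-day PDC, given the other model terms: not in the documents. It is assumed, with range 0.3 to 0.7.

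**The plan's own figure**

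Normal approximation: n per group = 2 × (1.960 + 1.036)² × 0.22² / 0.10² = 86.9, so 87. The exact two-sided t-test gives 88 per group with power 0.8505. The stated 88 is reproduced.

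**Effect of adding baseline PDC**

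1. SE of the treatment difference = 0.22 × √(1/104 + 1/126) × √(1 − r²) = 0.0291 × √(1 − r²).
2. With two equal subgroups, each subgroup-specific difference has SE √2 × SE. The interaction is the difference of two of these, so its SE is 2 × SE.
3. Power for an interaction of 0.10, two-sided 5%: Φ(0.10 / interaction SE − 1.96).
4. Equivalent gain in sample size: 1 / (1 − r²).

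| r (assumed) | SE of difference | Interaction SE | Power for 0.10 | Equivalent sample |
|---|---|---|---|---|
| no baseline PDC | 0.0291 | 0.0583 | 40% | 1.00 |
| 0.3 | 0.0278 | 0.0556 | 44% | 1.10 |
| 0.5 | 0.0252 | 0.0505 | 51% | 1.33 |
| 0.7 | 0.0208 | 0.0416 | 67% | 1.96 |

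The last row, for example: 0.10 / 0.0416 − 1.96 = 0.44, and Φ(0.44) = 0.67.

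With the full ITT of 110 v 127, power is 41% without baseline PDC and 45%, 52% or 69% with it, so the choice of denominator matters little.

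**Cost of missing baseline values**

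If a fraction m of patients has no baseline PDC and leaves the model, the SE is multiplied by √[(1 − r²) / (1 − m)]. The gain is used up when m = r², that is at 9%, 25% or 49% missing for r = 0.3, 0.5 or 0.7.

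**Limits of the illustration**

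SD 0.22 and 104 v 126 belong to summary PDC. Class PDC exists only for patients prescribed that class (SAP 5.6), so class-level samples are smaller and absolute power is lower at the same SD. The class-level SD is not given. Unequal subgroups lower power further.

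**The case against.** The strongest reply is that the baseline-adjusted treatment effect is already planned. The ANCOVA in SAP 7.8 covers summary PDC in both the ITT and PP populations, and SAP 7.10.1.1 carries it to each class. The sensitivity model has a different job: Protocol 11.4.1 describes supportive analyses that adjust for the stratification factors. This stands. A reader might infer that the plan never adjusts PDC for its baseline value, and the documents contradict that.

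Second, the omission may be one of wording. The sensitivity model is called AN(C)OVA although every listed term is categorical, so a covariate might have been carried over silently. The subgroup text does not list the treatment main effect either, so its list may not be complete. Against this, the sensitivity list repeats treatment and insurer data as if complete, and the subgroup text names a plain ANOVA. The text is ambiguous at best, and the same edit settles it.

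Third, the gain depends on an unknown correlation. SAP 1.3 asks for only four weeks of stable medication, while baseline PDC spans 183 days. A recently started class may therefore have a poor or absent baseline value. This stands as to size: at r = 0.3 interaction power moves only from 40% to 44%.

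Fourth, the covariate is not free. SAP 6.1 allows no substitution of missing values, so patients without a baseline value would leave the model. This stands, and the fix has to deal with it.

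Finally, a reader might extend the precision argument to the logistic model for mean PDC of at least 80%. It does not carry over: adjustment there changes the odds ratio being estimated and need not reduce its standard error.

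**Conclusion.** The point holds in a limited form. As written, the sensitivity model with the minimisation factors and the class-PDC subgroup ANOVAs do not name baseline PDC, and the subgroup models do not name insurer data. The loss falls on one sensitivity analysis and on interaction tests that SAP 7.11 calls exploratory.

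It would be wrong to infer that the trial's main result is affected. Omitting baseline PDC does not bias the treatment comparison, and neither the primary test nor the sample size uses these models. For insurer data the criticism is inconsistency with SAP 7.8; the documents give no figure from which an effect could be computed.

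For summary PDC, the standard error would be about 5%, 13% or 29% smaller at r = 0.3, 0.5 or 0.7. This rests on the planning SD of 0.22, at most 104 v 126 patients, equal subgroups and an assumed correlation. The direction holds for any non-zero correlation provided few baseline values are missing; the size cannot be taken from the documents. Even at r = 0.7 an interaction of 0.10 would be detected only about two times in three, so the subgroup analyses remain exploratory.

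**What to change.** - **SAP 7.11 and Protocol 11.4.5:** fit the PDC subgroup models as ANCOVA with treatment, subgroup, their interaction, insurer data (yes/no) and the matching baseline PDC (class value for class PDC, summary value for summary PDC) as a continuous fixed covariate. Name the model for summary PDC, which is not stated now.
- **SAP 7.8:** add baseline summary PDC to the sensitivity model as a continuous fixed covariate. The planned ANCOVA describes baseline adherence both as yes/no and as a random effect; bring that wording into line.
- **Missing baseline PDC:** either use a missing-value indicator, stated as an exception to SAP 6.1, or show the model without baseline PDC alongside. Report the number of patients without a baseline value per class and arm.
- **Logistic model for mean PDC of at least 80%:** no change is required by this point. If covariates are added, label the odds ratio as conditional.

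The cost is one degree of freedom per added term, a few lines of text and the missing-value rule. No new data are needed. The change should be fixed before the final analysis.
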